1. INTRODUCTION AND RATIONALE

Patients with acute pulmonary embolism (PE) usually have good outcomes.¹ However, their prognosis may vary dramatically according to whether the patient is hemodynamically stable. High-risk PE (5-7% of hospitalized patients with PE) is defined by hemodynamic instability and encompasses the clinical presentations of cardiac arrest, obstructive shock, or persistent hypotension.² These high risk patients have 30-day mortality rates ranging from 15% to as high as 77%. However, PE patients with respiratory failure that do not fulfill shock criteria, therefore currently not considered as high risk in the ESC guideline, also show a >30% risk of death and further respiratory failure.³⁻⁶ High-risk PE patients require immediate reperfusion therapy on top of anticoagulation. The standard reperfusion treatment in these patients is thrombolytic therapy (class 1-B, 2019 European Society of Cardiology (ESC) guidelines), administered at last in part at the Intensive Care Unit (ICU), with the idea of accelerated fragmentation of the thrombus by lytic medication given systemically.² This carries a significant risk of major bleeding (10-25%) and intracranial hemorrhage (ICH, 3%).² This risk has been shown to be a major barrier for administering lifesaving systemic thrombolysis in daily practice conditions, which has been suggested to contribute to the high mortality of these patients.⁷ The need to minimize the risk of serious bleeding or to offer alternatives to systemic thrombolysis in patients with a high bleeding risk has driven the development of alternative strategies for pulmonary reperfusion. Catheter-directed therapy (CDT), which includes catheter thrombectomy ("thrombectomy") may be associated with lower morbidity and mortality as it offers patients a fast and relatively safe relief of thrombus load and associated signs and symptoms, and may thus represent a better and safer option than systemic thrombolysis.

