To assess statistical power, the probability of the primary outcome was assumed to be 0.19 in the thrombectomy arm (based on the most recent data available) and 0.46 in the systemic thrombolysis arm (corresponding with a treatment OR of 3.71 and a risk difference of 27.5%; number needed to treat 3.6). The minimum clinically important difference was set at 27.5% based on discussion within the project group, scientific societies and patient representatives, and on clinical relevance for the difference facets of the composite endpoints. The assumed ARR of 27.5% consists of 5% decrease in mortality, 21.5% reduction in treatment failure or major bleeding and 1% reduction in ischemic stroke (the latter both based on expert opinion).¹⁸ Given a power of 80%, a two-sided α -level of 5%, and a 1:2 (systemic thrombolysis:CDT) patient allocation, 35 patients are needed in the systemic thrombolysis and 70 patients in the CDT arm. Assuming 5% drop-out, 37 patients (systemic thrombolysis) and 74 patients (CDT; total 111 patients) will be recruited. The calculation was done using G*Power (version 3.1.9.6) and is based on proportion difference tested with an anticipated OR.

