8.3 Study procedures

The study starts as soon as the patients is identified as eligible for inclusion and randomised. All patients, i.e. both study arms, will be treated with an UFH bolus after diagnosis. Patients randomised to the usual care arm will be treated with UFH or LMWH with systemic thrombolysis. Patient randomised to the intervention will be treated with UFH or LMWH (see paragraph 5.2 for specifics) and transferred to the cath lab and subjected to the thrombectomy. All further diagnostic tests (e.g. echocardiography, repeated blood test) are used along clinically relevant but not dictated by this protocol. No biomarkers or imaging test at baseline or follow-up will be required for the study. The SCAI SHOCK stage will be assessed at baseline and every 6 hours starting from randomization until the patient is stabilized and transferable to a normal ward (**Table 1**).^{26,27} At 48 hours following randomisation, the amount of oxygen supplementation (I O_2 /min) is noted in the medical chart. Patients will be contacted by the Sponsor on day 7 (± 2 days), at 3 months (± 1 week), at 6 months (± 1 week), at 9 months (± 1 week) and at 12 months (± 2 weeks) by e-mail to complete the PROMS questionnaire(s) (**Table 2**).

Stage	Α	В	С	D	E
Condition	Hemodynamically	Hemodynamically	Hypoperfusion	Failure to	Extremis /
	stable	unstable	= Shock	stabilize with	refractory shock
				initial therapy	
Hypotension:					
- SBP	>90 mm Hg	60-90 mm Hg	60-90 mm Hg	60-90 mm Hg	<60 mm Hg
- MAP	>65 mm Hg	50-65 mm Hg	50-65 mm Hg	50-65 mm Hg	<50 mm Hg
		OR	AND	AND	OR
Hypoperfusion					
- Arterial lac-					
tate	<2 mmol/L	2-5 mmol/L OR	2-5 mmol/L O R	>5-10 mmol/L	>10 mmol/L
			200-500 U/L	OR	OR
- ALAT	<200 U/L	200-500 U/L	≥ 7.2	>500 U/L	< 7.2
- рН	≥ 7.2	≥ 7.2		≥7.2	
		AND	AND	OR	OR
Treatment	No Drugs	No Drugs	No Drugs	2 Drugs	≥3 Drugs OR
intensity	No Devices	No Devices	No Devices		Device
			OR	OR	OR
			1 Drug without	1 Drug with	Out-of- or in-
			hypotension or	persistent	hospital cardiac
			hypoperfusion	hypotension or	arrest
				hypoperfusion	

Table 1: SCAI SHOCK stage overview. SBP = systolic blood pressure; MAP = mean arterial pressure; ALAT = alanine aminotransferase, Drugs = intravenous vaso-active drugs, Devices = RV support or VA-ECMO; hypotension = SBP ≤90 mm Hg or MAP ≤65 mm Hg

	7 Days	3 Months	6 Months	9 Months	1 Year
EQ-5D-5L	Х	Х	Х	Х	Х
ICHOM-VTE -	Х	Х	Х	Х	Х

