10.1 Primary study parameter(s)

For the primary composite endpoint, we will provide the cumulative incidence (number and percentage) for each trial arm and estimate the Odds Ratio (OR, including the 95% Confidence Interval using a binary logistic regression) to compare trial arms. In case of imbalance in background characteristics we can adjust the logistic regression analysis for the respective confounders.

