10.2 Secondary study parameter(s)

For continuous secondary endpoints (e.g., DOOR in the first 7 days after randomization), we will estimate mean or median difference between trial arms using an Independent Samples t

Test (mean difference) or a Mann Whitney-U test (median difference), depending on the normality of the distribution. Regarding categorical secondary outcomes, differences between the trial arms will be analyzed using a Chi-square test or Fisher's exact test, when appropriate. Repeated measures secondary outcomes are analyzed using mixed-effects (longitudinal) regression models. Outcomes will be (numerically) stratified according to the type of thrombectomy (FlowTriever vs. Indigo). A per-protocol analysis is performed as a sensitivity analysis. Both R studio and Graphpad software will be used for statistical analysis and making graphs, respectively. A two-sided p-value <0.05 is considered statistically significant. Missing data, where applicable, will be imputed with the use of multiple imputation under the missing-at-random assumption with chained equations. Outcome variables will not be imputed, as is the convention in randomized controlled trials. Patient safety will be monitored by a Data Safety Monitoring Board (DSMB) that will include several senior researchers. Subgroup analyses will be performed (if feasible, i.e. if numbers per subgroup are sufficiently large) for man versus women, age below 75 or 75 and older, different devices used and subtype of high-risk PE.

A cost effectiveness analysis (CEA) will be performed after a time horizon of one year for the primary outcome and QALYs. QALYs will be estimated using the EQ-5D-5L administered at day 7 and after 3, 6, 9 and 12 months, the Dutch tariff, and the "Area under the Curve" approach.^{28,29}

The economic evaluation will be performed in accordance with the 'Dutch Guideline for economic Evaluations'.¹⁸ In the main analysis, the societal perspective will be applied, meaning that all costs will be included irrespective of who pays or benefits (i.e. the cost of the intervention, other healthcare use, informal care, as well as productivity losses from unpaid and paid work). Intervention costs will be micro-costed, all other costs will be measured using cost questionnaires administered at 7 and after 3, 6, 9 and 12 months, and valued using standard prices provided by the 'Dutch Manual for Costing Studies in Health Care'.³⁰

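### Section 10.1 fixes an arm-only primary model with optional adjustment after imbalance is seen; one prespecified baseline severity covariate would settle the model and may add some power

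*Protocol*

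**What the plan says.** Section 10.1 reports the composite as a number and percentage per arm and will "estimate the Odds Ratio (OR, including the 95% Confidence Interval using a binary logistic regression) to compare trial arms". The following sentence says the model can be adjusted for the confounders concerned if background characteristics are unbalanced. It does not say which variables count, how much imbalance is needed, or whether the adjusted or the unadjusted result is then primary.

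Section 8.3 provides a baseline severity measure: "The SCAI SHOCK stage will be assessed at baseline and every 6 hours starting from randomization". The inclusion criteria (4.2) sort patients by entry route 2a to 2d: post cardiac arrest, obstructive shock, persistent hypotension, or respiratory failure with RV dysfunction and raised troponin. Section 10.2 lists among its subgroups "different devices used and subtype of high-risk PE". Randomisation is stratified by centre only (8.2). Section 10 defers fuller detail to a statistical analysis plan, which is not at hand.

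**The concern.** Two separate things are at stake.

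- **Precision.** A baseline variable that predicts the outcome improves the treatment comparison when it is in the model, whether or not the arms are balanced on it. A rule that brings severity in only after imbalance is noticed leaves it out of most trials, and any gain goes with it.
- **Openness of the primary model.** Adjustment is optional and depends on the data. Two analysts following 10.1 could report different primary odds ratios from the same trial and both be within the protocol.

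About 30 primary events are expected, so a modest gain in efficiency is worth having.

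**Working it through.** **Inputs (section 4.4).** CDT arm: "the probability of the primary outcome was assumed to be 0.19 in the thrombectomy arm". Control arm: "0.46 in the systemic thrombolysis arm (corresponding with a treatment OR of 3.71 and a risk difference of 27.5" (per cent). Power: "Given a power of 80" per cent. Two-sided alpha and allocation: "level of 5%, and a 1:2 (systemic thrombolysis:CDT) patient allocation". Size: 35 + 70, or 37 + 74 = 111 with 5% drop-out. The calculation compares two proportions and has no covariate.

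**Step 1: reproduce the plan's own figure.** Take p1 = 0.46, p2 = 0.19 and k = 2, so the pooled risk is (0.46 + 2 × 0.19)/3 = 0.28.

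n1 = [1.96 √(0.28 × 0.72 × 1.5) + 0.842 √(0.46 × 0.54 + 0.19 × 0.81/2)]² / 0.27² = (1.078 + 0.480)² / 0.0729 ≈ 33.3, so 34 + 68.

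- Power at 35 + 70 by this formula is 81.9%.
- The stated OR of 3.71 and difference of 27.5 points fit 0.465 v 0.19: (0.465/0.535)/(0.19/0.81) = 3.71. Fisher's exact power there is 78.9% at 34 + 68 and 80.5% at 35 + 70, which matches the stated 35 + 70.
- Inflating for 5% drop-out gives 37 + 74 = 111.

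The sample size stands as an unadjusted design.

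**Step 2: events available.** 35 × 0.46 + 70 × 0.19 = 16.1 + 13.3 = 29.4 events.

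**Step 3: power with and without severity at 35 + 70.** The protocol gives no prognostic strength, so it is varied. Marginal risks are held at the design values.

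*Simulation A:* four equal severity groups, one linear term, likelihood-ratio test, 6,000 trials per row.

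| Odds ratio, highest v lowest severity (assumed) | Unadjusted | Adjusted |
|---|---|---|
| 1 | 83.3% | 83.1% |
| 4 | 83.3% | 84.7% |
| 8 | 83.8% | 87.4% |
| 19 | 82.3% | 89.4% |

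*Simulation B:* four-level stage entered as categories, correlated with subtype, Wald test, 8,000 trials per row. The last column adjusts for stage only when its imbalance has chi-square p < 0.10. That threshold is assumed, because 10.1 gives none.

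| Within-arm c-statistic (assumed) | Unadjusted | Stage always in | Stage in only if unbalanced |
|---|---|---|---|
| 0.50 | 82.2% | 82.1% | 82.0% |
| 0.62 | 81.8% | 82.5% | 81.9% |
| 0.71 | 81.6% | 84.8% | 82.1% |
| 0.79 | 81.7% | 88.6% | 82.5% |

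The trigger fires in about 10% of trials, so the rule recovers almost none of the gain. An extreme c-statistic of 0.86 would give 81.4% to 92.9% with stage as a linear term, but nothing in the protocol suggests that strength.

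**Step 4: type I error.** Under the null, simulation A gave 5.1% adjusted (5.2% unadjusted) at an odds ratio of 19. Simulation B gave 4.8% to 5.1% with stage always in. A separate likelihood-ratio run gave 5.6%.

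**Step 5: shape of the relation.** Section 8.1.1 counts a SCAI stage that has not fallen as lack of improvement. A patient who starts at stage A cannot fall. A post-arrest patient is placed at stage E by Table 1 and cannot rise. Risk of the composite may therefore be high at both ends. With a U-shaped pattern (control risks 63/30/30/63%) a linear term gained nothing: 82.4% to 82.2%. In other U-shaped runs categorical coding gained about 2.5 and 5 points where the linear term again gained none.

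**Step 6: parameters.** Treatment plus a three-category covariate uses 3 terms, or 29.4/3 ≈ 10 events per term. Treatment plus all four subtypes uses 4 terms, about 7 per term. Four-level stage and subtype together use 7 terms, about 4 per term, which is too thin.

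**The case against.** The strongest reply is that nothing in 10.1 is an error. The protocol sizes an unadjusted comparison and plans one, the number reproduces, and covariates are commonly named in the analysis plan, which may do so here. Part of this stands: the point is missed efficiency. But 10.1 is not silent pending the analysis plan. It states an optional imbalance rule, and an analysis plan that names covariates would have to replace that rule.

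Several stronger readings are tempting and do not hold.

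- **A 7-point loss shown by the protocol's own figures.** Section 1 says "These high risk patients have 30-day mortality rates ranging from 15% to as high as 77" (per cent), and (0.77/0.23)/(0.15/0.85) ≈ 19 is the strong case in simulation A. That range is no anchor. It spans mortality rates from different reports, and the 77% is in-hospital mortality for all high-risk patients in one national dataset, not for a top severity stratum. The trial excludes catastrophic PE (4.3). Section 4.4 assigns only 5 of the 27.5 points to mortality.
- **SCAI stage known for every patient.** This is firm for subtype, since eligibility requires one of 2a to 2d. It is less firm for SCAI: Table 1 uses lactate, ALAT and pH, while 8.3 says the study itself demands no biomarkers.
- **The unadjusted odds ratio is biased.** It is a marginal odds ratio, and the trial was sized on it. The adjusted one is a different, conditional quantity: 3.63 marginal corresponds to about 4.4 at a c-statistic of 0.71 and 5.4 at 0.79.
- **The imbalance rule inflates type I error.** Applied mechanically in simulation B it gave 4.2% to 5.0%. The weakness is that the covariates, the trigger and the status of the adjusted result are left open.

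**Conclusion.** The point holds as a recommended improvement. Section 10.1 commits to an arm-only model with a discretionary adjustment after the data are seen, although a baseline severity variable is available for every patient. The gain in power from prespecifying it is about 0 points if severity is not prognostic, 1 to 4 if moderately prognostic and about 7 if strongly so, with type I error near 5%. These figures rest on assumed prognostic strength and shape and on the design risks of 0.46 and 0.19. The protocol supplies neither strength nor shape, so no single figure should be quoted as the loss. A reader might infer that the trial is underpowered. It is not on its own inputs: 35 + 70 gives about 80 to 82% without any covariate. Closing the choice of primary model is worthwhile even if the gain in power proves small.

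**What to change.** Replace the imbalance sentence in 10.1, and keep the analysis plan consistent with it, along these lines: the primary analysis is a logistic regression of the 30-day composite on allocated arm and one baseline severity covariate, fitted whether or not the arms appear balanced.

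1. **Choose one covariate.** Either the high-risk subtype 2a to 2d, with a rule set by the sponsor for patients who meet more than one criterion, or baseline SCAI stage, with a rule for missing laboratory components.
2. **Fix the coding before outcome data are seen.** A few collapsed categories are safer than a linear term, given the possible non-monotone relation.
3. **Report the covariate-standardised risk difference** with its confidence interval beside the adjusted odds ratio, so the result can be read against the 27.5-point target.
4. **Keep the unadjusted odds ratio** as a sensitivity analysis.

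Handling of centre, the stratification factor, is a separate matter.

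The cost is a sentence or two of text, with no new patients or visits. The downsides are small: the adjusted odds ratio is conditional and lies further from 1, and with about 30 events the covariate must use few parameters.

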10.2 Secondary study parameter(s)

For continuous secondary endpoints (e.g., DOOR in the first 7 days after randomization), we will estimate mean or median difference between trial arms using an Independent Samples t

Test (mean difference) or a Mann Whitney-U test (median difference), depending on the normality of the distribution. Regarding categorical secondary outcomes, differences between the trial arms will be analyzed using a Chi-square test or Fisher's exact test, when appropriate. Repeated measures secondary outcomes are analyzed using mixed-effects (longitudinal) regression models. Outcomes will be (numerically) stratified according to the type of thrombectomy (FlowTriever vs. Indigo). A per-protocol analysis is performed as a sensitivity analysis. Both R studio and Graphpad software will be used for statistical analysis and making graphs, respectively. A two-sided p-value <0.05 is considered statistically significant. Missing data, where applicable, will be imputed with the use of multiple imputation under the missing-at-random assumption with chained equations. Outcome variables will not be imputed, as is the convention in randomized controlled trials. Patient safety will be monitored by a Data Safety Monitoring Board (DSMB) that will include several senior researchers. Subgroup analyses will be performed (if feasible, i.e. if numbers per subgroup are sufficiently large) for man versus women, age below 75 or 75 and older, different devices used and subtype of high-risk PE.

A cost effectiveness analysis (CEA) will be performed after a time horizon of one year for the primary outcome and QALYs. QALYs will be estimated using the EQ-5D-5L administered at day 7 and after 3, 6, 9 and 12 months, the Dutch tariff, and the "Area under the Curve" approach.^{28,29}

The economic evaluation will be performed in accordance with the 'Dutch Guideline for economic Evaluations'.¹⁸ In the main analysis, the societal perspective will be applied, meaning that all costs will be included irrespective of who pays or benefits (i.e. the cost of the intervention, other healthcare use, informal care, as well as productivity losses from unpaid and paid work). Intervention costs will be micro-costed, all other costs will be measured using cost questionnaires administered at 7 and after 3, 6, 9 and 12 months, and valued using standard prices provided by the 'Dutch Manual for Costing Studies in Health Care'.³⁰

Cost and effect differences will be estimated, while appropriately accounting for the skewed nature of costs (bootstrapping), correlated costs and effects (bivariate regression model), missing data (multiple imputation), baseline imbalances (baseline adjustment), and the clustered nature of data (mixed model), if applicable.(38) Then, incremental cost-effectiveness ratios (ICER) will be calculated by dividing the difference in costs by the difference in effects. The uncertainty stratified around the ICER and will be estimated using bias-corrected and accelerated bootstrapping with 5.000 replications and graphically presented on cost-effectiveness planes. These planes will indicate the probability that an intervention is cost-effective compared to usual care at different values of willingness to pay (cost-effectiveness acceptability curve).²⁹ To assess the robustness of the results, various sensitivity analyses will Version 2.1: 16-12-2024 30 of 38

be performed (e.g. healthcare perspective, complete-case analysis, per-protocol analysis, human capital approach versus friction cost approach).²⁹

A budget impact analysis (BIA) will be conducted according to ZonMw's 'BIA, leidraad en rekentool' and ISPOR's principles of good practice.³¹ The budget impact analysis will be based on the Dutch population, and hence Dutch incidence data will be used. Perspectives that will be considered are the societal, government (Budget Kader Zorg), and insurer perspective. The cost of the intervention mix will be valued using Dutch standard costs for the societal perspective, actual NZA tariffs for the government perspective, and average tariffs NZA for the insurer perspective. Different scenarios will be evaluated including the following: 1) the intervention is not implemented, i.e. all patients will receive usual care, 2) the intervention is offered to the whole patient population. These subgroups will be defined based on the results of the study, e.g. subgroups who particularly benefitted from the intervention (e.g., type of thrombectomy, sex, presence of cancer). Uncertainty will be estimated using probabilistic sensitivity analyses.

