8.5 Replacement of individual subjects after withdrawal

The study will be continued until 111 patients have been randomized and completed the first 30 days of follow-up (or met the primary outcome within that period).

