10. STATISTICAL ANALYSIS

The data will be analyzed on an ITT basis in several steps. The ITT populations consist of all subjects who have been randomized, i.e. when the subject number and allocated regimen are recorded in the eCRF. Patients will be analyzed in accordance with the randomized treatment assignment irrespective of the factual implementation of the assigned treatment regimen. The baseline characteristics in each trial arm will be described. Continuous variables will be described as mean with standard deviation (SD) or median with interquartile range (IQR) for continuous variables depending on their normality of distribution. The Shapiro–Wilk test will be used to assess normality. Categorical variables are presented as numbers and percentages. On top of the ITT analyses a per-protocol (safety population) analysis will be performed. A detailed description of the statistical analysis will be provided in the Statistical Analysis Plan.

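### With outcome imputation barred and day-30 status analysed by logistic regression, patients lost event-free leave the primary analysis while patients lost after an event stay; the odds ratio is biased only if that loss differs by arm

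*Protocol*

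**What the plan says.** All references are to the Protocol.

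- **Analysis set (section 10).** "The ITT populations consist of all subjects who have been randomized", analysed as assigned. Section 8.6 applies intention to treat to the primary outcome.
- **Primary analysis (section 10.1).** Cumulative incidence per arm, and an odds ratio with 95% confidence interval from binary logistic regression. Adjustment is possible if baseline characteristics are imbalanced. No method that uses partial follow-up is named.
- **Missing data (section 10.2).** Missing data are multiply imputed under missing at random, but "Outcome variables will not be imputed, as is the convention in randomized controlled trials". The sentence stands under secondary parameters, yet it is not restricted to them; the software and significance level are given in the same paragraph.
- **Economic evaluation (section 10.2).** Here the plan provides for "missing data (multiple imputation") when estimating cost and effect differences.
- **Continuation of the trial (section 8.5).** The study runs until 111 patients have been randomised and "completed the first 30 days of follow-up (or met the primary outcome within that period").
- **Sample size (section 4.4).** 35 + 70 evaluable patients, raised for 5% drop-out to 37 + 74 = 111 recruited.
- **Withdrawal (section 8.4).** Patients may leave at any time.

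**The concern.** Whether a patient enters the primary analysis depends on the outcome. An event seen before loss fixes the composite as positive, and the patient stays. Without an event, day-30 status is unknown. Logistic regression cannot use that patient, and scoring the patient as event-free would itself be an imputation, which section 10.2 forbids. Observed event-free follow-up is thrown away, and the numerator keeps every observed event while the denominator shrinks.

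At stake are the arm-specific 30-day risks and the risk difference, which are reported or derived from the cumulative incidences. If loss differs by arm, the odds ratio is affected too. Unequal loss is conceivable in an open-label trial with withdrawal at any time. The only reason given for the rule is convention, which does not address this selection.

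Section 8.5 uses the same asymmetric criterion to decide who counts towards 111, although section 4.4 already put the drop-out allowance into that number.

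**Working it through.** **Inputs (section 4.4).** "the probability of the primary outcome was assumed to be 0.19 in the thrombectomy arm" and "0.46 in the systemic thrombolysis arm (corresponding with a treatment OR of 3.71 and a risk difference of 27.5"%. The printed 0.46 is rounded: 0.19 + 0.275 = 0.465, and (0.465/0.535)/(0.19/0.81) = 3.71. I use 0.465.

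**The plan's own figure.** With 35 and 70 patients, 0.465 v 0.19, two-sided 5%, the exact unconditional power of Fisher's test is 80.5%. Inflation: 35/0.95 = 36.8, so 37; 70/0.95 = 73.7, so 74; total 111. The sample size reproduces and is not in question.

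**Effect of dropping event-free losses.** Let p be the true 30-day risk and d the fraction of event-free patients lost, all assumed to stay event-free. Then:

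- complete-case risk = p / (p + (1 − p)(1 − d));
- complete-case odds = [p/(1 − p)] / (1 − d);
- complete-case odds ratio = true odds ratio × (1 − d for CDT)/(1 − d for thrombolysis).

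Equal d therefore cancels from the odds ratio exactly.

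| Event-free patients lost (thrombolysis / CDT) | Risks | Risk difference | Odds ratio |
|---|---|---|---|
| 0 / 0 | 46.5% v 19.0% | 27.5 points | 3.71 |
| 5% / 5% | 47.8% v 19.8% | 28.0 | 3.71 |
| 10% / 10% | 49.1% v 20.7% | 28.5 | 3.71 |
| 10% / 0 (assumed) | 49.1% v 19.0% | 30.1 | 4.12 |
| 0 / 10% (assumed) | 46.5% v 20.7% | 25.8 | 3.33 |

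**A different definition of loss.** Suppose 5% of all patients in each arm are lost, every one of them event-free. The observed risk is then p/(1 − 0.05): 0.465/0.95 = 48.9% and 0.19/0.95 = 20.0%, with odds ratio 3.84. It moves because 5% of everyone is 0.05/0.535 = 9.3% of the event-free in one arm and 0.05/0.81 = 6.2% in the other. On this definition, an assumed 10% in one arm only gives 4.56 or 3.25.

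**Illustration near the significance boundary (Wald p from the 2×2 table, thrombolysis v CDT).** Complete cases of 13/35 v 13/70 give p = 0.041. Restoring two and four missing patients with one event, in CDT, gives 13/37 v 14/74, p = 0.064. One event in each arm gives 14/37 v 14/74, p = 0.033. Near the design rates, 16/35 v 13/70 gives p = 0.004; even if all four missing CDT patients had events and neither missing thrombolysis patient did (16/37 v 17/74), p = 0.030.

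**Section 8.5 against section 4.4.** Section 4.4 needs 105 with a known outcome and recruits 111. Read literally, section 8.5 asks for 111 with a known outcome. At 5% loss that means 111/0.95 = 116.8, about 117 randomised.

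**The case against.** Several points on the other side stand.

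- **The odds ratio is robust to equal loss.** A reader might infer from the overstated risks that the treatment effect is inflated. On the planned effect measure it is not, if the same proportion of event-free patients is lost in each arm. The documents give no figure for unequal loss; the 10% is an assumption.
- **The p-value example is chosen at the boundary.** A reader might infer that the trial's conclusion hangs on one missing patient. The first table is not a design scenario, Fisher's test on it already gives 0.054, and one event in each arm makes the result more significant. It also assumes that lost patients have events, whereas overstated risks assume that they do not.
- **Intention to treat is not redefined.** A reader might infer that the protocol excludes these patients from the analysis set. It never says so. The loss follows from sections 10.1 and 10.2 taken together and is a missing-data choice. It does leave the promise to analyse all randomised patients unmet.
- **The 5% is not shown to be event-free loss.** Section 4.4 does not define drop-out, and it may include refusal of deferred consent (exclusion 15), where the data may not be used.
- **Section 8.5 is a recruitment rule**, not an analysis set. The economic evaluation is also a separate analysis, so a different method there does not by itself show the primary rule to be wrong.
- **Sensitivity analyses may stand in the SAP**, which is not at hand. Their absence from the protocol is not held against it here.

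What does not stand is the defence that the whole matter belongs to the SAP. The protocol itself fixes the rule.

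**Conclusion.** The point holds as a moderate one that should be corrected. The stated rule, combined with logistic regression on day-30 status, selects patients by outcome and does not deliver an analysis of everyone randomised.

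If lost patients stay event-free, arm risks and the risk difference are overstated, by about half a point in the difference when 5% of event-free patients are lost in each arm. The odds ratio is biased only when event-free loss differs by arm, in either direction according to which arm loses more. If lost patients do go on to have events, the overstatement shrinks or reverses. At the planned level of drop-out the expected effect is small.

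The mismatch between sections 8.5 and 4.4 is a separate matter of wording and does not depend on any of these assumptions.

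**What to change.** 1. **Replace the sentence for the primary outcome.** Any component observed before loss counts as an event. Patients who are event-free at last contact, and whose data may be used, are kept by multiple imputation of day-30 status conditional on being event-free up to that contact, using arm and baseline severity. This keeps the odds ratio. Time of last contact should enter as that condition, not as an ordinary predictor, because event-free completers all sit at day 30.
2. **Optional supporting analysis.** A Kaplan-Meier 30-day risk per arm. Death lies inside the composite, so it is not a competing risk, but the estimate still assumes non-informative censoring and so does not cure informative loss.
3. **Tipping-point analysis by arm.** Vary the event risk of the lost patients separately in each arm, and report where the conclusion changes.
4. **Consent refusals.** Patients whose data may not be used cannot be recovered by imputation. Report their number by arm.
5. **Drop the appeal to convention.**
6. **Reconcile section 8.5 with section 4.4.** State whether 111 is the number randomised, including the 5% allowance for 105 evaluable, or the number with a known 30-day outcome.

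The cost is protocol and SAP wording, a little extra analysis, and a missing-at-random assumption that the tipping-point analysis then probes. No new data are needed, and no extra patients if 111 is confirmed as the number randomised. It should be settled before outcome data are seen by arm.
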